## Appendix

Acute kidney injury Dx			
ICD10	ICD9	ICD10 Description	ICD9 Description
I120	40391	Hypertensive chronic kidney disease with stage 5 chronic kidney disease or end stage renal disease	Hypertensive chronic kidney disease, unspecified, with chronic kidney disease stage V or end stage renal disease
N170	5845	Acute kidney failure with tubular necrosis	Acute kidney failure with lesion of tubular necrosis
N171	5846	Acute kidney failure with acute cortical necrosis	Acute kidney failure with lesion of renal cortical necrosis
N172	5847	Acute kidney failure with medullary necrosis	Acute kidney failure with lesion of renal medullary [papillary] necrosis
N178	5848	Other acute kidney failure	Acute kidney failure with other specified pathological lesion in kidney
N179	5849	Acute kidney failure, unspecified	Acute kidney failure, unspecified
N19	586	Unspecified kidney failure	Renal failure, unspecified
Z4931	V560	Encounter for adequacy testing for hemodialysis	Encounter for extracorporeal dialysis
Angioedema Dx			
ICD10	ICD9	ICD10 Description	ICD9 Description
T783XX9951		Angioneurotic edema, initial encounter	Angioneurotic edema, not elsewhere classified
T783XX1V5889		Angioneurotic edema, subsequent encounter	Other specified aftercare
T783XX99099		Angioneurotic edema, sequela	Late effect of other and unspecified external causes
Chronic kidney disease stage IV or V or dialysis Dx			
ICD10	ICD9	ICD10 Description	ICD9 Description
E1021	25043	Type 1 diabetes mellitus with diabetic nephropathy	Diabetes with renal manifestations, type I [juvenile type], uncontrolled
E1022	25041	Type 1 diabetes mellitus with diabetic chronic kidney disease	Diabetes with renal manifestations, type I [juvenile type], not stated as uncontrolled
E1029	25041	Type 1 diabetes mellitus with other diabetic kidney complication	Diabetes with renal manifestations, type I [juvenile type], not stated as uncontrolled
E1065	25043	Type 1 diabetes mellitus with hyperglycemia	Diabetes with renal manifestations, type I [juvenile type], uncontrolled
E1121	25042	Type 2 diabetes mellitus with diabetic nephropathy	Diabetes with renal manifestations, type II or unspecified type, uncontrolled
E1122	25040	Type 2 diabetes mellitus with diabetic chronic kidney disease	Diabetes with renal manifestations, type II or unspecified type, not stated as uncontrolled
E1129	25040	Type 2 diabetes mellitus with other diabetic kidney complication	Diabetes with renal manifestations, type II or unspecified type, not stated as uncontrolled
E1165	25042	Type 2 diabetes mellitus with hyperglycemia	Diabetes with renal manifestations, type II or unspecified type, uncontrolled
E1321	25040	Other specified diabetes mellitus with diabetic nephropathy	Diabetes with renal manifestations, type II or unspecified type, not stated as uncontrolled
E1322	25040	Other specified diabetes mellitus with diabetic chronic kidney disease	Diabetes with renal manifestations, type II or unspecified type, not stated as uncontrolled
E1329	25040	Other specified diabetes mellitus with other diabetic kidney complication	Diabetes with renal manifestations, type II or unspecified type, not stated as uncontrolled
I120	40391	Hypertensive chronic kidney disease with stage 5 chronic kidney disease or end stage renal disease	Hypertensive chronic kidney disease, unspecified, with chronic kidney disease stage V or end stage renal disease
I129	40390	Hypertensive chronic kidney disease with stage 1 through stage 4 chronic kidney disease, or unspecified chronic kidney disease	Hypertensive chronic kidney disease, unspecified, with chronic kidney disease stage I through stage IV, or unspecified
I130	40491	Hypertensive heart and chronic kidney disease with heart failure and stage 1 through stage 4 chronic kidney disease, or unspecified chronic kidney disease	Hypertensive heart and chronic kidney disease, unspecified, with heart failure and with chronic kidney disease stage I through stage IV, or unspecified
I1310	40490	Hypertensive heart and chronic kidney disease without heart failure, with stage 1 through stage 4 chronic kidney disease, or unspecified chronic kidney disease	Hypertensive heart and chronic kidney disease, unspecified, without heart failure and with chronic kidney disease stage I through stage IV, or unspecified
I1311	40492	Hypertensive heart and chronic kidney disease without heart failure, with stage 5 chronic kidney disease, or end stage renal disease	Hypertensive heart and chronic kidney disease, unspecified, without heart failure and with chronic kidney disease stage V or end stage renal disease
I132	40493	Hypertensive heart and chronic kidney disease with heart failure and with stage 5 chronic kidney disease, or end stage renal disease	Hypertensive heart and chronic kidney disease, unspecified, with heart failure and chronic kidney disease stage V or end stage renal disease
N181	5851	Chronic kidney disease, stage 1	Chronic kidney disease, Stage I
N182	5852	Chronic kidney disease, stage 2 (mild)	Chronic kidney disease, Stage II (mild)
N183	5853	Chronic kidney disease, stage 3 (moderate)	Chronic kidney disease, Stage III (moderate)
N184	5854	Chronic kidney disease, stage 4 (severe)	Chronic kidney disease, Stage IV (severe)
N189	5859	Chronic kidney disease, unspecified	Chronic kidney disease, unspecified
N250	5880	Renal osteodystrophy	Renal osteodystrophy
N251	5881	Nephrogenic diabetes insipidus	Nephrogenic diabetes insipidus
N2581	58881	Secondary hyperparathyroidism of renal origin	Secondary hyperparathyroidism (of renal origin)
N2589	58889	Other disorders resulting from impaired renal tubular function	Other specified disorders resulting from impaired renal function
N259	5889	Disorder resulting from impaired renal tubular function, unspecified	Unspecified disorder resulting from impaired renal function
End-Stage Renal Disease (ESRD) Dx			
ICD10	ICD9	ICD10 Description	ICD9 Description
I953	45821	Hypotension of hemodialysis	Hypotension of hemodialysis
N185	5855	Chronic kidney disease, stage 5	Chronic kidney disease, Stage V

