## 2. Outcomes

- a. Effectiveness endpoint:
  - i. Primary: a composite of all-cause death or HF hospitalization
    - Note cardiovascular death was not used because National Death Index data were only available up to 2016. Instead, all-cause death was used.
    - HF hospitalization is defined as HF diagnosis primary position in the inpatient dataset
  - ii. Secondary: individual components separately
- b. Safety endpoint:
  - i. Primary: a composite of SAE, defined as any hospitalization or ED visit due to diagnosis codes in the primary position:
    - hypotension
    - acute kidney injury/acute kidney failure
    - hyperkalemia
    - angioedema
  - ii. Secondary: individual components

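### The Appendix's acute kidney injury list includes end-stage kidney disease and hemodialysis codes, and two of its three angioedema ICD-9 descriptions do not name angioedema (minor code-list error)

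*Protocol*

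**What the plan says.** The Appendix prints diagnosis code lists. Under the AKI heading, the first row is I120/40391, described as "Hypertensive chronic kidney disease with stage 5 chronic kidney disease or end stage renal disease". The last is Z4931, "Encounter for adequacy testing for hemodialysis", paired with ICD-9 code V560, "Encounter for extracorporeal dialysis".

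The chronic kidney disease list repeats I120/40391. The end-stage renal disease list repeats Z4931 with the same ICD-10 description but pairs it with V5631.

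The angioedema list has three rows. All three ICD-10 descriptions name angioneurotic edema. On the ICD-9 side the first does too, but the second reads "Other specified aftercare" and the third "Late effect of other and unspecified external causes".

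Study Population, item 3, refers to the Appendix for the eligibility codes. Item 3.h excludes AKI and advanced chronic kidney disease or dialysis as separate conditions, both over [-60, 0] days. It excludes angioedema over all data up to day 0. Outcomes, item b.i, defines the primary safety endpoint as "a composite of SAE, defined as any hospitalization or ED visit due to diagnosis codes in the primary position", with AKI and angioedema among its four components. It does not cite the Appendix.

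**The concern.** A list headed acute kidney injury should identify acute kidney events. Two of its rows describe chronic end-stage disease or a dialysis encounter, and the Appendix itself classifies both ICD-10 codes as chronic elsewhere. A list headed angioedema should not pick up patients through generic aftercare or late-effect codes.

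Two uses are at stake. The stated one is eligibility, where a wrong code excludes the wrong patients. The possible one is the safety outcome. If the same AKI list is applied to follow-up claims, a primary-position claim for end-stage kidney disease or dialysis would be counted as an acute event, both in the primary safety composite and in the AKI secondary endpoint.

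**Working it through.** There is no plan figure to reproduce, so the check sets the lists side by side.

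**AKI list, 8 rows.** N170, N171, N172, N178 and N179 are acute kidney failure (5 rows). N19/586 is unspecified kidney failure (1 row). The remaining 8 − 5 − 1 = 2 rows are:

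| AKI row | ICD-10 code elsewhere | ICD-9 code elsewhere |
|---|---|---|
| I120 / 40391 | Chronic kidney disease list | 40391, same list |
| Z4931 / V560 | End-stage renal disease list | V560 on neither kidney list; Z4931 is paired there with V5631 |

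The double filing is therefore complete for I120/40391. For the dialysis row it holds only on the ICD-10 side, where the partner codes also disagree.

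**Angioedema list, 3 rows.** Two of the three ICD-9 descriptions do not name the condition. The code cells run together in the text at hand, so V5889 and 9099 are readings of joined cells. The descriptions are intact, and the point rests on them. These are shares of rows, not of patients or events.

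**Eligibility, kidney codes.** Let A be the AKI codes, C the chronic kidney disease codes and D the dialysis/end-stage codes. A patient is excluded by any code in A ∪ C ∪ D within [-60, 0] days. This takes D to feed the dialysis exclusion; whether the protocol says so is a separate question. Because the window is the same, a code excludes the same patient whichever list holds it. I120/40391 is in A and C, and Z4931 is in A and D. V560 is in A only, so it excludes patients only through the AKI list. Deleting it without adding it to D would change eligibility.

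**Eligibility, angioedema codes.** The look-back runs from the beginning of the data, and data from 2014 are used. Wherever ICD-9 claims are searched, an aftercare or late-effect code at any earlier time removes a patient. The rule uses only information up to day 0 and applies to both arms, so the expected cost is sample size. The protocol gives no counts.

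**Safety outcome, if the AKI list is used there.** Let a and b be the true AKI event rates on ARNI and ARB, and f₁ and f₀ the added false ones. The observed ratio is (a + f₁)/(b + f₀).
- If f₁ = f₀ > 0, the ratio moves toward 1.
- If f₁/a = f₀/b, the ratio does not change.
- Otherwise it can move either way.

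The protocol gives none of these four quantities, so neither direction nor size can be derived. Within the composite, false AKI events are diluted by the other three components, so any effect is more visible on the AKI secondary endpoint.

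**The case against.** The strongest objection is that the outcome harm rests on a link the protocol does not make. Item 3 cites the Appendix for eligibility and item 3.e for the heart failure wash-out, but Outcomes b.i cites it for no safety component, and outcome code lists are commonly left to a statistical analysis plan. This stands. That it is the only AKI list printed makes its use for the outcome plausible, not established.

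The second is that few such events would qualify even so. The code must be in primary position on a hospital or emergency claim, and an adequacy-testing visit is an unlikely reason for either. Patients with chronic kidney disease or dialysis codes in the prior 60 days are excluded, and the printed exclusion list also holds earlier-stage codes such as N181 to N183. Every participant has heart failure, and I132, "Hypertensive heart and chronic kidney disease with heart failure and with stage 5 chronic kidney disease, or end stage renal disease", is not on the AKI list. This also stands. What remains are patients whose kidney disease was coded only before the 60 days or progresses during follow-up.

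Third, V560 does not say chronic, so removing it from the outcome loses any acute dialysis coded only that way. That is a real cost of the fix.

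A reader might infer that the primary safety hazard ratio is biased toward 1, or that the misfiled kidney codes exclude the wrong patients. The documents support neither. The first needs the unstated link and similar absolute false-event rates in both arms; the second fails because the exclusion windows coincide.

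**Conclusion.** The lists are wrong as printed, and the point is minor. It is certain that 2 of 8 AKI rows are chronic or dialysis entries, that Z4931 has two different ICD-9 partners, and that 2 of 3 angioedema ICD-9 descriptions do not name angioedema.

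Under the stated use, the only consequence is that the generic angioedema entries can exclude patients without angioedema. The loss is unknown and probably small, and it depends on how far ICD-9 claims are searched. The kidney entries do not alter eligibility as printed.

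The outcome consequence is conditional on the AKI list defining the safety component. Given that, the effect on the primary safety composite is probably negligible and falls mainly on the AKI secondary endpoint. That is a judgement from the restrictions above, not a computed result.

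**What to change.** 1. For the safety outcome, use an AKI list without I120/40391 and Z4931/V560.
2. Add V560 to the dialysis/end-stage exclusion list, so that its removal from the AKI list leaves eligibility unchanged.
3. Reconcile the two ICD-9 pairings of Z4931 (V560 and V5631).
4. Remove the two angioedema ICD-9 entries that do not name angioedema, after checking their codes against the source table.
5. State in Outcomes b.i which lists define the safety components.

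This is an edit to code lists plus one sentence. The downside is that acute dialysis recorded only as V560 would no longer count as an AKI event. Removing the angioedema entries can only keep or enlarge the eligible cohort.

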## Appendix

N186	5856	End stage renal disease	End stage renal disease
T82818 A	99673	Embolism due to vascular prosthetic devices, implants and grafts, initial encounter	Other complications due to renal dialysis device, implant, and graft
T82828 A	99673	Fibrosis due to vascular prosthetic devices, implants and grafts, initial encounter	Other complications due to renal dialysis device, implant, and graft
T82838 A	99673	Hemorrhage due to vascular prosthetic devices, implants and grafts, initial encounter	Other complications due to renal dialysis device, implant, and graft
T82848 A	99673	Pain due to vascular prosthetic devices, implants and grafts, initial encounter	Other complications due to renal dialysis device, implant, and graft
T82858 A	99673	Stenosis of other vascular prosthetic devices, implants and grafts, initial encounter	Other complications due to renal dialysis device, implant, and graft
T82868 A	99673	Thrombosis due to vascular prosthetic devices, implants and grafts, initial encounter	Other complications due to renal dialysis device, implant, and graft
T82898 A	99673	Other specified complication of vascular prosthetic devices, implants and grafts, initial encounter	Other complications due to renal dialysis device, implant, and graft
T85611 A	99656	Breakdown (mechanical) of intraperitoneal dialysis catheter, initial encounter	Mechanical complication due to peritoneal dialysis catheter
T85621 A	99656	Displacement of intraperitoneal dialysis catheter, initial encounter	Mechanical complication due to peritoneal dialysis catheter
T85631 A	99656	Leakage of intraperitoneal dialysis catheter, initial encounter	Mechanical complication due to peritoneal dialysis catheter
T85691 A	99656	Other mechanical complication of intraperitoneal dialysis catheter, initial encounter	Mechanical complication due to peritoneal dialysis catheter
T8571X A	99668	Infection and inflammatory reaction due to peritoneal dialysis catheter, initial encounter	Infection and inflammatory reaction due to peritoneal dialysis catheter
T8610	99681	Unspecified complication of kidney transplant	Complications of transplanted kidney
T8611	99681	Kidney transplant rejection	Complications of transplanted kidney
T8612	99681	Kidney transplant failure	Complications of transplanted kidney
T8613	99681	Kidney transplant infection	Complications of transplanted kidney
T8619	99681	Other complication of kidney transplant	Complications of transplanted kidney
Z4822	V420	Encounter for aftercare following kidney transplant	Kidney replaced by transplant
Z4901	V561	Encounter for fitting and adjustment of extracorporeal dialysis catheter	Fitting and adjustment of extracorporeal dialysis catheter
Z4902	V562	Encounter for fitting and adjustment of peritoneal dialysis catheter	Fitting and adjustment of peritoneal dialysis catheter
Z4931	V5631	Encounter for adequacy testing for hemodialysis	Encounter for adequacy testing for hemodialysis
Z4932	V568	Encounter for adequacy testing for peritoneal dialysis	Encounter for other dialysis
Z9115	V4512	Patient's noncompliance with renal dialysis	Noncompliance with renal dialysis
Z940	V420	Kidney transplant status	Kidney replaced by transplant
Z992	V4511	Dependence on renal dialysis	Renal dialysis status

### End-Stage Renal Disease (ESRD) Px

ICD10	ICD9	ICD10 Description	ICD9 Description
03130JD	3993	Bypass Right Subclavian Artery to Upper Arm Vein with Synthetic Substitute, Open Approach	Insertion of vessel-to-vessel cannula
03130Z D	3927	Bypass Right Subclavian Artery to Upper Arm Vein, Open Approach	Arteriovenostomy for renal dialysis
03140JD	3993	Bypass Left Subclavian Artery to Upper Arm Vein with Synthetic Substitute, Open Approach	Insertion of vessel-to-vessel cannula
03140Z D	3927	Bypass Left Subclavian Artery to Upper Arm Vein, Open Approach	Arteriovenostomy for renal dialysis
031509 V	3927	Bypass Right Axillary Artery to Superior Vena Cava with Autologous Venous Tissue, Open Approach	Arteriovenostomy for renal dialysis
03150A V	3927	Bypass Right Axillary Artery to Superior Vena Cava with Autologous Arterial Tissue, Open Approach	Arteriovenostomy for renal dialysis
03150JD	3993	Bypass Right Axillary Artery to Upper Arm Vein with Synthetic Substitute, Open Approach	Insertion of vessel-to-vessel cannula
03150JV	3927	Bypass Right Axillary Artery to Superior Vena Cava with Synthetic Substitute, Open Approach	Arteriovenostomy for renal dialysis
03150K V	3927	Bypass Right Axillary Artery to Superior Vena Cava with Nonautologous Tissue Substitute, Open Approach	Arteriovenostomy for renal dialysis
03150Z D	3927	Bypass Right Axillary Artery to Upper Arm Vein, Open Approach	Arteriovenostomy for renal dialysis
03150Z V	3927	Bypass Right Axillary Artery to Superior Vena Cava, Open Approach	Arteriovenostomy for renal dialysis

## Appendix

031609 V	3927	Bypass Left Axillary Artery to Superior Vena Cava with Autologous Venous Tissue, Open Approach	Arteriovenostomy for renal dialysis
03160A V	3927	Bypass Left Axillary Artery to Superior Vena Cava with Autologous Arterial Tissue, Open Approach	Arteriovenostomy for renal dialysis
03160JD	3993	Bypass Left Axillary Artery to Upper Arm Vein with Synthetic Substitute, Open Approach	Insertion of vessel-to-vessel cannula
03160JV	3927	Bypass Left Axillary Artery to Superior Vena Cava with Synthetic Substitute, Open Approach	Arteriovenostomy for renal dialysis
03160K V	3927	Bypass Left Axillary Artery to Superior Vena Cava with Nonautologous Tissue Substitute, Open Approach	Arteriovenostomy for renal dialysis
03160Z D	3927	Bypass Left Axillary Artery to Upper Arm Vein, Open Approach	Arteriovenostomy for renal dialysis
03160Z V	3927	Bypass Left Axillary Artery to Superior Vena Cava, Open Approach	Arteriovenostomy for renal dialysis
031709 V	3927	Bypass Right Brachial Artery to Superior Vena Cava with Autologous Venous Tissue, Open Approach	Arteriovenostomy for renal dialysis
03170A V	3927	Bypass Right Brachial Artery to Superior Vena Cava with Autologous Arterial Tissue, Open Approach	Arteriovenostomy for renal dialysis
03170JD	3993	Bypass Right Brachial Artery to Upper Arm Vein with Synthetic Substitute, Open Approach	Insertion of vessel-to-vessel cannula
03170JV	3927	Bypass Right Brachial Artery to Superior Vena Cava with Synthetic Substitute, Open Approach	Arteriovenostomy for renal dialysis
03170K V	3927	Bypass Right Brachial Artery to Superior Vena Cava with Nonautologous Tissue Substitute, Open Approach	Arteriovenostomy for renal dialysis
03170Z D	3927	Bypass Right Brachial Artery to Upper Arm Vein, Open Approach	Arteriovenostomy for renal dialysis
03170Z V	3927	Bypass Right Brachial Artery to Superior Vena Cava, Open Approach	Arteriovenostomy for renal dialysis
031809 V	3927	Bypass Left Brachial Artery to Superior Vena Cava with Autologous Venous Tissue, Open Approach	Arteriovenostomy for renal dialysis
03180A V	3927	Bypass Left Brachial Artery to Superior Vena Cava with Autologous Arterial Tissue, Open Approach	Arteriovenostomy for renal dialysis
03180JD	3993	Bypass Left Brachial Artery to Upper Arm Vein with Synthetic Substitute, Open Approach	Insertion of vessel-to-vessel cannula
03180JV	3927	Bypass Left Brachial Artery to Superior Vena Cava with Synthetic Substitute, Open Approach	Arteriovenostomy for renal dialysis
03180K V	3927	Bypass Left Brachial Artery to Superior Vena Cava with Nonautologous Tissue Substitute, Open Approach	Arteriovenostomy for renal dialysis
03180Z D	3927	Bypass Left Brachial Artery to Upper Arm Vein, Open Approach	Arteriovenostomy for renal dialysis
03180Z V	3927	Bypass Left Brachial Artery to Superior Vena Cava, Open Approach	Arteriovenostomy for renal dialysis
03190JF	3993	Bypass Right Ulnar Artery to Lower Arm Vein with Synthetic Substitute, Open Approach	Insertion of vessel-to-vessel cannula
03190ZF	3927	Bypass Right Ulnar Artery to Lower Arm Vein, Open Approach	Arteriovenostomy for renal dialysis
031A0J F	3993	Bypass Left Ulnar Artery to Lower Arm Vein with Synthetic Substitute, Open Approach	Insertion of vessel-to-vessel cannula
031A0Z F	3927	Bypass Left Ulnar Artery to Lower Arm Vein, Open Approach	Arteriovenostomy for renal dialysis
031B0JF	3994	Bypass Right Radial Artery to Lower Arm Vein with Synthetic Substitute, Open Approach	Replacement of vessel-to-vessel cannula
031B0Z F	3927	Bypass Right Radial Artery to Lower Arm Vein, Open Approach	Arteriovenostomy for renal dialysis
031C0JF	3994	Bypass Left Radial Artery to Lower Arm Vein with Synthetic Substitute, Open Approach	Replacement of vessel-to-vessel cannula
031C0Z F	3927	Bypass Left Radial Artery to Lower Arm Vein, Open Approach	Arteriovenostomy for renal dialysis
03LK0C Z	3953	Occlusion of Right Internal Carotid Artery with Extraluminal Device, Open Approach	Repair of arteriovenous fistula
03LK0Z Z	3953	Occlusion of Right Internal Carotid Artery, Open Approach	Repair of arteriovenous fistula
03LK3C Z	3953	Occlusion of Right Internal Carotid Artery with Extraluminal Device, Percutaneous Approach	Repair of arteriovenous fistula
03LK3Z Z	3953	Occlusion of Right Internal Carotid Artery, Percutaneous Approach	Repair of arteriovenous fistula

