## STUDY POPULATION

1. Study population (see Figure 2) is created for each calendar interval.
2. Initiation of ARNI or comparator (ARB)
  - a. ARB: any of azilsartan, candesartan, eprosartan, Irbesartan, losartan, Olmesartan, telmisartan, valsartan
  - b. Index date (day 0): prescription fill from July 7, 2015

3. Assessment of eligibility (eligibility assessment window: [-365, 0] days) – See Appendix for list of codes.
  - a. Continuous enrollment for medical and drug insurance (Part A, B, and D)
  - b. Diagnosis of HF (outpatient diagnosis x2 or inpatient x1)
  - c. Reduced EF (<45%) algorithm (5)
  - d. No prior use of ARNI or comparator (exposure wash-out window: [-365, -1] days)
  - e. No recent HF hospitalization, defined as HF diagnosis (Appendix) in the primary position in the inpatient dataset (outcome wash-out window: [-60, 0] days)
  - f. No recent nursing facility stay, defined as any of the following claims in [-60, 0] days
    - i. Place of service: 31 (skilled nursing facility), 32 (nursing facility), 33 (custodial care facility)
    - ii. CPT codes: 99301, 99302, 99303, 99311, 99312, 99313, 99315, 99316, 99379, 99380, G0066
  - g. Excluded if age <65 years or exposure to both drugs on day 0
  - h. Contraindication to either drug (exclusion assessment window: [-60, 0] days, unless specified otherwise)
    - i. Hypotension
    - ii. Chronic kidney disease stage IV or V or dialysis
    - iii. Acute kidney injury
    - iv. Hyperkalemia
    - v. Angioedema: [-beginning of data, 0] days
  - i. If a patient meets the above-mentioned eligibility criteria more than once, only the first record will be included.

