03VK3C Z	3953	Restriction of Right Internal Carotid Artery with Extraluminal Device, Percutaneous Approach	Repair of arteriovenous fistula
03VK4C Z	3953	Restriction of Right Internal Carotid Artery with Extraluminal Device, Percutaneous Endoscopic Approach	Repair of arteriovenous fistula
03VL0C Z	3953	Restriction of Left Internal Carotid Artery with Extraluminal Device, Open Approach	Repair of arteriovenous fistula
03VL3C Z	3953	Restriction of Left Internal Carotid Artery with Extraluminal Device, Percutaneous Approach	Repair of arteriovenous fistula
03VL4C Z	3953	Restriction of Left Internal Carotid Artery with Extraluminal Device, Percutaneous Endoscopic Approach	Repair of arteriovenous fistula
03WY0J Z	3994	Revision of Synthetic Substitute in Upper Artery, Open Approach	Replacement of vessel-to-vessel cannula
03WY3J Z	3994	Revision of Synthetic Substitute in Upper Artery, Percutaneous Approach	Replacement of vessel-to-vessel cannula
03WY4J Z	3994	Revision of Synthetic Substitute in Upper Artery, Percutaneous Endoscopic Approach	Replacement of vessel-to-vessel cannula
03WYX JZ	3994	Revision of Synthetic Substitute in Upper Artery, External Approach	Replacement of vessel-to-vessel cannula
05HY33 Z	3895	Insertion of Infusion Device into Upper Vein, Percutaneous Approach	Venous catheterization for renal dialysis
06HY33 Z	3895	Insertion of Infusion Device into Lower Vein, Percutaneous Approach	Venous catheterization for renal dialysis
0TS00Z Z	5561	Reposition Right Kidney, Open Approach	Renal autotransplantation
0TS10Z Z	5561	Reposition Left Kidney, Open Approach	Renal autotransplantation
0TY00Z 0	5569	Transplantation of Right Kidney, Allogeneic, Open Approach	Other kidney transplantation
0TY00Z 1	5569	Transplantation of Right Kidney, Syngeneic, Open Approach	Other kidney transplantation

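### The Appendix ESRD lists, apparently the source for the dialysis exclusion, include carotid-artery codes and generic device and graft codes that do not identify dialysis or kidney failure

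*Protocol*

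**What the plan says.** Protocol, Study Population, item 3 refers the reader to the Appendix: "See Appendix for list of codes". Item 3.h sets the exclusions under "Contraindication to either drug (exclusion assessment window: [-60, 0] days, unless specified otherwise"), and 3.h.ii names "Chronic kidney disease stage IV or V or dialysis".

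The Appendix has a diagnosis list with the same title as 3.h.ii. It also has two ESRD lists, one of diagnoses and one headed "End-Stage Renal Disease (ESRD) Px". Each row pairs an ICD-10 code with an ICD-9 code. The ESRD lists contain rows such as:

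- "Occlusion of Right Internal Carotid Artery with Extraluminal Device, Open Approach" and "Restriction of Left Internal Carotid Artery with Extraluminal Device, Open Approach", both paired with ICD-9 3953, repair of an arteriovenous fistula;
- "Insertion of Infusion Device into Upper Vein, Percutaneous Approach", paired with ICD-9 3895, a venous catheter placed for dialysis;
- "Stenosis of other vascular prosthetic devices, implants and grafts, initial encounter", paired with ICD-9 99673, complications of a dialysis device or graft.

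Neither the text nor the Appendix requires a second, renal code before one of these rows counts.

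**The concern.** A code list behind an exclusion should select the patients that the exclusion names. In these rows the two halves disagree. The ICD-9 side describes dialysis access or a fistula repair. The ICD-10 side describes a neck-artery procedure, or a device or graft that could serve any purpose.

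Two things are at stake. First, older adults with HFrEF may have vascular disease, grafts or infusion lines without renal failure, and the list removes them under a label that does not describe them. Second, for the venous, 03PY and graft rows, the exclusion is narrow on a claim coded in ICD-9 and broad on one coded in ICD-10. The stated criterion therefore does not have one meaning throughout the data.

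**Working it through.** The protocol gives no patient count for this exclusion, so the check is a reading and count of the Appendix rows.

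**Step 1: which list serves 3.h.ii.** The list titled like 3.h.ii holds diagnoses only. It reaches stage 5 disease through the hypertensive codes I120, I1311 and I132, but it has no dialysis-status or dialysis-procedure code and omits N185. N185, Z992 and the 5A1D codes stand only in the ESRD lists. Two dialysis-related diagnoses, Z4931 and I953, recur in the lists for acute kidney injury and hypotension, which serve other criteria. No criterion or outcome calls for an ESRD list by name. Without the ESRD lists, the dialysis half of 3.h.ii would have almost no codes.

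**Step 2: count of the ESRD procedure list by ICD-10 group.**

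| Group | Codes | ICD-9 partner |
|---|---|---|
| Arm artery-to-vein bypass (031x) | 40 | 3927, 3993, 3994 |
| Internal carotid occlusion (03LK, 03LL) | 12 | 3953 |
| Internal carotid restriction (03VK, 03VL) | 6 | 3953 |
| 03PY removal, tissue substitute | 6 | 3943 (dialysis shunt) |
| 03PY removal, synthetic substitute | 3 | 3994 |
| 03WY revision | 4 | 3994 |
| Infusion device, upper or lower vein | 2 | 3895 (dialysis catheter) |
| Kidney reposition or transplant (0TS, 0TY) | 8 | 5561, 5569 |
| Peritoneal dialysis and haemodialysis (3E1M, 5A1D) | 4 | 5498, 3995 |

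Total: 40 + 12 + 6 + 6 + 3 + 4 + 2 + 8 + 4 = 85.

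**Step 3: the mismatched rows.**

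- Carotid: 12 + 6 = 18, and 18/85 = 21%. The ICD-10 text names a different vessel and procedure from a fistula repair for dialysis.
- Generic in ICD-10, dialysis-specific in ICD-9: 2 + 6 = 8 procedure codes, and 8/85 = 9%.
- ESRD diagnosis list: 28 codes, of which 7 (T82818A to T82898A: embolism, fibrosis, haemorrhage, pain, stenosis, thrombosis, other specified) concern vascular prostheses in general and are paired with 99673. 7/28 = 25%.

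**Step 4: consequence.** Under the rule as written, one such code in [-60, 0] days is enough to exclude. These are shares of codes, not of patients. The number of patients cannot be computed from the protocol.

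**The case against.** The strongest reply has four parts.

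- *The link is not stated.* The list that carries the title of 3.h.ii is the CKD diagnosis list, and no sentence assigns the ESRD lists to it. This stands as a caveat. The inference is still the only reading that makes the dialysis exclusion workable, and stating the link belongs in the fix.
- *The effect is small.* The window is 60 days and the rule applies to both arms at baseline. Some of these patients would also be removed by the CKD list, which includes stages 1 to 3. This stands. It limits the point to the definition of the population.
- *Lack of a renal word proves little.* By ICD-10 description, 85 − 12 = 73 of the 85 procedure codes name no dialysis or kidney condition; only the 0TS, 0TY, 3E1M and 5A1D codes do. This also stands. The 40 bypass codes fall among the 73 but describe the artery-to-vein anatomy of dialysis access and should remain. The test has to be whether the ICD-10 entry fits its ICD-9 partner and the criterion, not whether it contains a particular word.
- *Removing generic codes may cost sensitivity.* The seven T82 codes are the list's only ICD-10 counterparts to 99673, and the two venous codes the only ones to 3895. That no dialysis patient would be lost is not shown.

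A reader might also infer that any venous line or any vascular-graft complication triggers exclusion. The lists do not go that far. They hold two percutaneous infusion-device codes, neither described as a central line, and seven types of complication. The generic T82 rows do not include infection or mechanical failure of a vascular graft.

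**Conclusion.** The point holds as a minor error in the code lists. It is clearest for the 18 internal carotid codes (21% of the procedure list), which do not fit a dialysis exclusion. It also holds, less sharply, for 8 procedure codes and 7 diagnosis codes that are broader in ICD-10 than in the ICD-9 codes paired with them.

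The conclusion assumes that the ESRD lists implement 3.h.ii and that a single code suffices, since no concurrent-code rule is given. That the number of patients is small is a judgement from the 60-day window, not a calculation. A reader might infer a biased hazard ratio, but the protocol does not support that: the exclusion is applied before matching and to both arms. What is affected is who is studied, and whether the exclusion means the same thing under both coding systems.

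**What to change.** In the Appendix and item 3.h.ii:

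1. Delete the 18 carotid codes (03LK, 03LL, 03VK, 03VL) from the ESRD procedure list.
2. Count 05HY33Z, 06HY33Z, the six 03PY tissue-substitute codes and the seven T82 codes only with a concurrent ESRD or dialysis code, such as N186, Z992 or a 5A1D code.
3. Define concurrent. Those confirming codes already exclude a patient on their own, so if they must fall in the same 60 days the rule amounts to deleting the generic codes. The generic codes keep a role only if confirmation may come from the longer [-365, 0] eligibility window.
4. Keep the arm artery-to-vein bypass codes.
5. State that the ESRD lists implement item 3.h.ii.

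The cost is an Appendix edit, one rerun of the cohort query, and a possible small loss of sensitivity for dialysis patients who are identified only by the generic codes. Counting excluded patients by triggering code in the rerun would show how much the change matters.
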